### **9.4.2 Adverse events severity/intensity**

For both AEs and SAEs, the Investigator must assess the severity / intensity of the event.

Grading will be performed using the Division of AIDS (DAIDS) Table for Grading the Severity of Adult and Pediatric Adverse Events, Version 2.0. [November 2014].

Citation: U.S. Department of Health and Human Services, National Institutes of Health, National Institute of Allergy and Infectious Diseases, Division of AIDS. Division of AIDS (DAIDS) Table for Grading the Severity of Adult and Pediatric Adverse Events, Version 2.0. [November 2014]. Available from:

[http://rsc.techres.com/Document/safetyandpharmacovigilance/DAIDS\\_AE\\_GRADING\\_TABLE\\_v2\\_NOV2014.pdf](http://rsc.techres.com/Document/safetyandpharmacovigilance/DAIDS_AE_GRADING_TABLE_v2_NOV2014.pdf)

In case of events or laboratory abnormalities not included in the table, the following scale will be used:

**Grade 1 (mild):** Symptoms causing no or minimal interference with usual social & functional activities

**Grade 2 (moderate):** Symptoms causing greater than minimal interference with usual social & functional activities

**Grade 3 (severe):** Symptoms causing inability to perform usual social & functional activities

**Grade 4 (potentially life-threatening):** Symptoms causing inability to perform basic self-care functions OR Medical or operative intervention indicated to prevent permanent impairment, persistent disability, or death

**Grade 5 (death):** Any AE where the outcome is death.

The term “severe” is often used to describe the intensity of a specific event (as in mild, moderate or severe myocardial infarction); the event itself, however, may be of relatively minor medical significance (such as severe headache). This criterion is *not* the same as “serious” which is based on subject/event *outcome* or *action* criteria associated with events that pose a threat to a subject’s life or functioning.

Seriousness, not severity, serves as a guide for defining regulatory obligations.

#### 9.4.3 Seriousness

A SAE is any AE occurring at any dose that:

- Results in death;
- Is life-threatening (i.e., in the opinion of the Investigator, the subject is at immediate risk of death from the AE);
- Requires inpatient hospitalization or prolongation of existing hospitalization (hospitalization is defined as an inpatient admission, regardless of length of stay);
- Results in persistent or significant disability/incapacity (a substantial disruption of the subject’s ability to conduct normal life functions);
- Is a congenital anomaly/birth defect;
- Constitutes an important medical event.

Important medical events are defined as those occurrences that may not be immediately life threatening or result in death, hospitalization, or disability, but may jeopardize the subject or require medical or surgical intervention to prevent one of the other outcomes listed above. Medical and scientific judgment should be exercised in deciding whether such an AE should be considered serious.

Events **not considered** to be SAEs are hospitalizations for:

- Routine treatment or monitoring of the studied indication not associated with any deterioration in condition.
- Hospitalization or prolongation of hospitalization for technical, practical, or social reasons, in absence of an AE.
- A procedure that is planned (i.e., planned prior to starting of treatment on study); must be documented in the source document and the CRF. Hospitalization or prolonged hospitalization for a complication remains a reportable SAE.
- An elective treatment of a pre-existing condition unrelated to the studied indication.
- Emergency outpatient treatment or observation that does not result in admission, unless fulfilling other seriousness criteria above.

If an AE is considered serious, both the AE page/screen of the CRF and the SAE Report Form must be completed.

For each SAE, the Investigator will provide information on severity, start and stop dates, relationship to IMP, action taken regarding IMP, and outcome.

#### 9.4.4 Duration

For both AEs and SAEs, the Investigator will provide a record of the start and stop dates of the event.

#### **9.4.5 Action Taken**

The Investigator will report the action taken with IMP as a result of an AE or SAE, as applicable (e.g., discontinuation of IMP) and report if concomitant and/or additional treatments were given for the event.

#### **9.4.6 Outcome**

Any SAE will be followed preferably until:

- Resolution of the event;
- Stabilization of the event; or
- Resetting the baseline situation of the event, in case baseline situation is available.

Otherwise, they will continue until:

- The event can be attributed to products other than the study medication or factors unrelated to the study; or
- It is unlikely to obtain further information.

[figure not shown]
### **9.5 PROCEDURE FOR REPORTING ADVERSE EVENTS**

#### **9.5.1 Immediate reporting by Investigator to sponsor**

The investigator will immediately notify the study sponsor of any serious and/or unexpected adverse events.

The report will be realized during the first 24 hours since the start of the serious adverse event. Notification will be made by means of the adverse events reporting form contained in Appendix IV of this protocol.

**Contact details for Sponsor:**

Contact details for Pharmacovigilance: Pharmacovigilance Department of MSD Spain (fax to [name]).

All adverse events will be recorded, regardless of the imputability (i.e., causal) relationship involved, in the corresponding adverse events description form. The latter is found in the CRF of each participant in the study.

The Sponsor will provide investigators with a copy of the annual periodic safety report e.g. Development Update Safety Report (DSUR) at the time of submission to the Regulatory Authority and Ethics Committee.

#### **9.5.2 Reporting to Regulatory Authorities and the Ethics Committee**

The sponsor will inform the Spanish Drug Agency (Ministry of Health), the competent authorities of the autonomous region and the Ethics Committees implicated in the clinical trial about any important information of security of the investigational medicinal product.

The sponsor will inform the Spanish Drug Agency (Ministry of Health) of any SUSAR which may be related to the study treatment.

The sponsor will inform competent authorities of the implicated autonomous region of any SUSAR which may be related to the study treatment, and that have been happened in patients in its autonomous region.

The Sponsor will inform relevant Regulatory Authorities;

- Of all relevant information about SUSAR that are fatal or life-threatening as soon as possible, and in any case no later than 7 days after knowledge of such a case. Relevant follow-up information for these cases will be subsequently be submitted within an additional eight days

- Of all other SUSAR as soon as possible, but within a maximum of 15 days of first knowledge by the investigator.

The sponsor will keep a detailed register of all the adverse events notified by the investigators.

All adverse events will be notified in table form in the final report of the clinical trial.

#### **9.6 ABNORMAL LABORATORY PARAMETERS**

An abnormal laboratory parameter shall be considered an AE if the abnormality:

- results in withdrawal from the study
- requires treatment, dose modification or investigational drug interruption or any other therapeutical intervention
- is considered clinically important

Regardless of their severity, only laboratory abnormalities that meet criteria of seriousness should be recorded as SAE.

If the laboratory abnormality is part of a diagnosis or syndrome, only the syndrome or diagnosis will be included as AE or SAE. If the laboratory abnormality is not part of a diagnosis or syndrome, it shall be recorded as AE or SAE.

Clinically significant changes in safety parameters that are associated with the disease under study will not be rated as AE or SAE, unless the investigator judges that are more severe than expected given the patient's condition.

#### **9.7 PREGNANCY**

The cases of pregnancy shall be recorded as AE and should only be considered as SAE only if they meet any seriousness criteria. Pregnancy is also a protocol deviation requiring premature termination of the patient. The investigator will provide medical support to the pregnant patient.

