### **7.2 EXCLUSION CRITERIA**

1. PI/r monotherapy
2. INSTI therapy during the previous 6 months
3. Evidence of previous INSTI resistance
4. Creatine clearance  $<50$  mL/min
5. Child-Pugh B or C
6. History of active uncontrolled GI disorders or diseases including:
  - 6.1. Major surgery of the GI tract, with the exception of cholecystectomy and appendectomy, in the previous 5 years.
  - 6.2. Any major bowel resection at any time
  - 6.3. Any chronic digestive disease such as peptic ulcer, Crohn's disease, ulcerative colitis, coeliac disease, confirmed intolerance to lactose or indeterminate colitis.
  - 6.4. Persistent infectious gastroenteritis, colitis or gastritis; persistent or chronic diarrhea of unknown etiology; *Clostridium difficile* infection (recurrent) or *Helicobacter pylori* infection (untreated);
  - 6.5. Irritable bowel syndrome (moderate-severe)
  - 6.6. Chronic constipation
  - 6.7. Active proctitis
7. Antibiotic therapy within the previous 2 months
8. In women, pregnancy or breastfeeding\*.

\* Female subjects of childbearing potential must not be pregnant, not be planning a pregnancy or breastfeeding. Sexually active women must be willing to use an effective method of contraception (hormonal contraception, diaphragm, intra-uterine device (IUD), or anatomical sterility in self or partner) from baseline until the end of the clinical trial. Sexually active men in heterosexual relationships must be willing to use an effective method of contraception (anatomical sterility in self) or agree on the use of an effective method of contraception by his partner (hormonal contraception, diaphragm, intra-uterine device, or anatomical sterility) from baseline until the end of the clinical trial.

*\* condom use is considered as an additional method of contraception only and cannot be the only method of contraception used as not been considered an effective method by the Clinical Trial Facilitation Group (CTFG) guidelines.*

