## 8.5 ASSESSMENTS FLOW-CHART

VISITS	SCR	BL	W12	W24	W48	VF
Window			+/- 2 weeks	+/- 2 weeks	+/- 2 weeks	
Inclusion/exclusion criteria	✓					
Patient informed form and Informed consent	✓					
Pregnancy test	✓ B			✓		
Randomization		✓				
Clinical visit		✓	✓	✓	✓	
Adherence questionnaire		✓	✓	✓	✓	
HIV-1 Viral load	✓ C	✓	✓	✓	✓	✓
Biochemistry	✓ C	✓ C	✓	✓	✓	
Hematology	✓ C	✓ C	✓	✓	✓	
CD4/CD8 cells count		✓ C	✓	✓	✓	
Stool sample		✓	✓	✓	✓	
Whole blood simple for IRSIA		✓	✓	✓	✓	
Adverse Events		✓	✓	✓	✓	
Concomitant medication		✓	✓	✓	✓	
Genotypic testing						✓

A **blood sample** (5 x 10 mL EDTA tubes, from which irsiCaixa will obtain 4 plasma vials and as many PBMCs as possible)

B Women of childbearing potential, within 10 days prior to randomization.

C Parameters performed within 2 months prior to Baseline will be accepted.

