## 9 ADVERSE EVENTS

### 9.1 DEFINITION

**Adverse event:** (AE) Medical event presented by a patient or clinical research subject administered a pharmaceutical product, and which does not necessarily have a causal relation to the treatment.

**Serious adverse event:** (SAE) Medical event classified as such and which, regardless of the dose involved:

- causes patient death,
- produces a life-threatening situation for the patient,
- requires or prolongs in hospital admission,
- produces important or persistent incapacitation/handicap, or constitutes a congenital defect or anomaly,
- needs action to prevent any of above situations, or
- is considered medically significant

Examples of such events are intensive care in an Emergency Service or in the home in a patient with allergic bronchospasm; blood dyscrasias or seizures not giving rise to hospital admission, or the development of drug dependency or abuse.

**Unexpected adverse event:** (UAE) AE related to the product in investigation the nature or intensity of which does not coincide with the information available on the product administered (IB or SmPC).

**Serious Unexpected Adverse Reaction:** (SUSAR) SAE related to the product in investigation the nature or intensity of which does not coincide with the information available on the product administered (IB or SmPC).

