### 9.2 MONITORING, RECORDING AND REPORTING OF ADVERSE EVENTS

An AE is any noxious, unintended, or untoward medical occurrence that may appear or worsen in a subject during the course of a study. It may be a new intercurrent illness, a worsening concomitant illness, an injury, or any concomitant impairment of the subject's health, including laboratory test values (as specified by the criteria below), regardless of etiology. Any worsening (i.e., any clinically significant adverse change in the frequency or intensity of a pre-existing condition) should be considered an AE. A diagnosis or syndrome should be recorded on the AE page of the CRF rather than the individual signs or symptoms of the diagnosis or syndrome.

An overdose, accidental or intentional, whether or not it is associated with an AE, or abuse, withdrawal, sensitivity or toxicity to an investigational product should be reported as an AE. If an overdose is associated with an AE, the overdose and AE should be reported as separate terms.

All subjects will be monitored for AEs during the study. Assessments may include monitoring of any or all of the following parameters: the subject's clinical symptoms, laboratory, pathological, radiological or surgical findings, physical examination findings, or other appropriate tests and procedures.

All AEs will be recorded by the Investigator from the time the subject signs informed consent until the last study visit or to 28 days after the last dose of IMP in case of early withdrawal while patient is receiving IMP. AEs and SAEs will be recorded on the AE page of the eCRF and in the subject's source documents. All SAEs must be reported to the Sponsor (see contact details at the end of the paragraph) within 24 hours of the Investigator's knowledge of the event by facsimile, or other appropriate method, using the SAE Report Form (Appendix IV, can be found in the Investigator's File), or approved equivalent form.

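### Collection of a birth outcome after study-drug exposure is not assured: pregnancy is a non-serious AE by default, the patient is terminated, and AE recording closes well before term

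*Combined protocol and SAP*

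**What the plan says.** All references are to the combined protocol and SAP.

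- **Seriousness.** A birth defect is a seriousness criterion in two places: 9.1 ("produces important or persistent incapacitation/handicap, or constitutes a congenital defect or anomaly") and 9.4.3 ("Is a congenital anomaly/birth defect").
- **Pregnancy.** Section 9.7 states: "The cases of pregnancy shall be recorded as AE and should only be considered as SAE only if they meet any seriousness criteria". It then ends participation: "Pregnancy is also a protocol deviation requiring premature termination of the patient". The only further provision is: "The investigator will provide medical support to the pregnant patient".
- **Recording window.** Under 9.2, recording of AEs starts once consent is signed and runs as follows: "until the last study visit or to 28 days after the last dose of IMP in case of early withdrawal while patient is receiving IMP".
- **Follow-up to outcome.** Section 9.4.6 sets this out for SAEs only. Section 9.4.4 asks for start and stop dates for AEs and SAEs alike. Section 7.3.3 gives patients who stop treatment early one examination with the tests of that visit.
- **Testing and contraception.** The flow chart in 8.5, as extracted, marks the pregnancy test at screening ("Women of childbearing potential, within 10 days prior to randomization") and at week 24. Section 7.2 requires contraception from baseline to the end of the trial. Section 6.3 sets 48 weeks of dosing from randomization.

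**The concern.** Each rule is ordinary on its own; the difficulty lies in the combination. A pregnancy enters the database as a non-serious AE, so it does not attract the follow-up in 9.4.6. Termination starts the 28-day clock in 9.2. The seriousness criterion most specific to pregnancy can usually be judged only at or near birth, after that clock has run out. Applied as written, the cut-off loses an outcome that the protocol itself calls serious.

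What is at stake is safety information on a product that 5.1 describes as non-authorized and 6.1 as a non-marketed formulation. The SUSAR clocks in 9.5.2 run from knowledge of a case, so they depend on someone learning of the event. Nothing here bears on the richness endpoint, power or type I error.

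**Working it through.** The plan gives no figure of its own on this point, so the check is a timeline.

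**Inputs from the documents**
- Dosing: 48 weeks (6.3).
- Visit windows: plus or minus 2 weeks (8.5), so the week-24 visit falls in weeks 22–26 and the week-48 visit in weeks 46–50.
- Screening pregnancy test: up to 10 days before randomization (8.5, footnote B).
- Recording: 28 days after the last dose for early withdrawal on study drug; last study visit for completers (9.2).

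**Assumptions not in the documents**
- Term is about 38 weeks (38 × 7 = 266 days) from conception.
- The last dose is taken on the day the pregnancy is found. Each extra day of dosing would move the cut-off by one day.

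**Formulas**
- Days to term when found = 266 − (day found − day of conception).
- Days to term when recording closes = the above − 28 for early withdrawal, or − 0 for a completer at the last visit.

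| Conception | Found | Days elapsed | Days to term when found | Days to term when recording closes |
|---|---|---|---|---|
| 10 days before baseline | week 26 | 182 + 10 = 192 | 74 | 46 |
| baseline | week 24 | 168 | 98 | 70 |
| baseline | week 26 | 182 | 84 | 56 |
| week 20 | week 24 | 28 | 238 | 210 |
| week 22 | week 50 (last visit) | 196 | 70 | 70 (42 if a 28-day tail is allowed) |

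The last row is a pregnancy that begins just after an early week-24 test and comes to light at a late week-48 visit. No test is marked there, so it would be found by other means. As a completer, she has no 28-day tail under 9.2.

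**Sensitivity to the definition of term.** Take 37 weeks' gestation counted from two weeks before conception, which is 35 weeks or 245 days from conception. The two tightest cases, both with a 28-day tail, become:
- conceived 10 days before baseline, found at week 26: 245 − 192 − 28 = 25 days left;
- conceived at week 22, found at week 50: 245 − 196 − 28 = 21 days left.

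Recording still closes before term in every case.

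**Testing gap.** Dosing after the last marked test runs from 48 − 26 = 22 weeks to 48 − 22 = 26 weeks.

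**The case against.** The strongest reply is that the reporting duties have no end date. Section 9.5.1 requires notice of serious or unexpected events, 9.5.2 runs from knowledge of a case, 9.4.4 asks for a stop date for every AE, and 9.7 keeps the investigator in contact through medical support. An early loss, or an anomaly recognised before birth and inside the window, would be recorded, and an SAE arising inside the window would be followed under 9.4.6. All of this stands. A reader might infer that a birth defect could never reach the SAE or SUSAR process; the documents do not support that. But none of these sections asks anyone to collect the birth outcome, and a stop date does not lengthen the window in 9.2.

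Other stronger readings also fail:

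- **A 28-day limit for everyone.** It applies only to early withdrawal on study drug.
- **A contradiction over partner pregnancies.** Section 7.2 asks men for contraception or to "agree on the use of an effective method of contraception by his partner", but gives no reason for this, and partners are not trial subjects under the AE definition in 9.1.
- **A missing week-48 test as an error.** No section promises one: 9.7 sets no testing schedule, and 8.4 has its listed tests done as needed at the flow-chart points. The observation also depends on where one tick sits in an extracted table.
- **20 to 28 weeks of dosing after the last test.** That is the interval between visits (46 − 26 to 50 − 22). Dosing is fixed at 48 weeks, which gives 22 to 26.

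Finally, Appendices I, II and IV appear only as titles and consent pages were removed. A pregnancy form or follow-up consent may exist there, although 9.7 refers to none.

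**Conclusion.** The concern holds in limited form. The rules in 9.2, 9.4.6 and 9.7, read together, do not assure collection of an outcome that 9.1 and 9.4.3 define as serious. In the scenarios above, about 70 days or more remain to term when the pregnancy is found, against a recording tail of 28 days or none. This rests on the assumed 38 weeks to term and on dosing stopping when the pregnancy is found; taking term as 37 weeks' gestation shortens the margin but does not remove it. A delivery well before term could fall inside the window.

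The expected number of cases among 60 patients, with pregnancy excluded and contraception required, is small. This is an inexpensive improvement to safety data, with no effect on the efficacy analysis. The testing gap of 22 to 26 weeks is a secondary matter for reconciliation, not a demonstrated contradiction.

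**What to change.** Reconcile 9.2, 9.4.3, 9.4.6 and 9.7 so that they state how the outcome of an exposed pregnancy is collected:

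1. Except pregnancies exposed to study drug from the 9.2 cut-off, for data collection only, whether the patient withdrew early or completed.
2. Record the pregnancy outcome and the infant's status.
3. Report any congenital anomaly as an SAE whenever it is found.
4. If an appendix already holds a pregnancy form or follow-up consent, cite it in 9.7.

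Separately, reconcile the pregnancy-test row in 8.5 with the contraception period in 7.2 and the termination rule in 9.7; no test visit is proposed here. The sponsor may also consider whether to collect partner pregnancies, with the partner's consent.

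The cost is a wording amendment, a report form and a few follow-up contacts.

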## 10 STATISTICS

Statistical analysis will be conducted by IrsiCaixa. A computerized database for the study will be created, which will be used for data analysis. Statistical analysis will be carried out using R.

A general analysis of all variables in the study will be conducted, including demographic and clinical characteristics at baseline.

### 10.1 STATISCAL ANALYSIS

- Taxonomic and functional diversity within (alpha-diversity) and between samples (beta-diversity) will be determined. Rarefaction curves will be generated to evaluate sampling efficiency. Diversity measures, reflecting the richness of the microbiome in terms of number of species and abundance of each species will be calculated. This will enable comparisons between groups and timepoints. Ordination methods including principal component analysis and phylum abundance within individuals will be used to check for significant differences between groups. Bacterial abundance and functional profiles will be analyzed with LEFSe. Univariate correlations involving >2 groups will be done applying ANOVA plus Tukey-Kramer post-hoc tests and Benjamini-Hochberg correction; 2-group comparisons will be performed with the Welch's t-test. The relationship between the microbiome and markers of immune activation, inflammation, tissue damage and bacterial translocation will require the application of nonlinear Kernel regression methods.
- Subjects requiring antibiotics for their clinical management during follow-up will not be excluded from the analyses, but the type, duration and reasons for antibiotic intake will be recorded and taken into account in association analyses. Results in HIV-1-infected subjects will be compared to the gut microbiome profiles of healthy HIV-1-negative individuals previously reported by the EU FP7-funded MetaHIT consortium. We will also use microbial ecology theory to describe ecological networks between microbes and between them and the host (degree distribution, clustering coefficient, distance, centrality, community structure, connectivity index, etc.).

*For extensive examples of microbiome analyses available and performed previously by our group at irsiCaixa, please see: Noguera-Julian, M. et al. Gut microbiota linked to sexual preference and HIV infection. EBioMedicine (2016) <http://dx.doi.org/10.1016/j.ebiom.2016.01.032>.*

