### 5.3 ENDPOINTS

#### 5.3.1 Primary endpoint(s)

- Increase in bacterial richness (observed species) at week 48, relative to baseline (week 0).

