#### 5.3.2 Secondary endpoints

- Longitudinal changes in:
  - Gut bacterial composition
  - Gut bacterial function
  - Other estimators of richness and diversity: Chao1, ACE, Shannon, 1/Simpson.
- Association of the gut microbiome composition and richness with:
  - Inflammation: IL-6, IP-10

- Coagulation: D-Dimer
- Enterocyte damage: Intestinal Fatty Acid Binding Protein (I-FABP)
- Bacterial translocation and monocyte activation: LPS-binding protein (LBP), soluble CD14.
- Maturation, activation, exhaustion and immune senescence in CD4+ and CD8+ T-cells: CD3+, CD4+, CD8+, CD45RA, CCR7, CD28, CD27, HLA-DR, CD38, PD-1, CD57.
- CD4 and CD8+ counts
- CD4+/CD8+ ratio
- In case of changes in the microbiome, the quantification of viral reservoir will be done in PBMCs.

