## 5.4 MEASURES TO AVOID BIAS

### 5.4.1 Randomization

Once eligibility has been confirmed, study participants will be assigned sequentially into the two treatment groups (intensification with RAL or placebo) through a randomization schedule based on the randomization plan using dedicated computer software.

Merck Sharpe & Dohme Co. will provide to the un-blinded correspondent with the CID randomization schedule that will list the grouping description and ID number. The randomization will be centralized in the CRO FLS-Research Support. The investigator

will phone to the CRO to inform about the eligibility of a patient and if he/she is on treatment with PI/r/c or NRTI/NNRTI-based. The CRO will add the patient to the randomization list, they will assign a code number to the patient and will inform to the Pharmacy Service the group where the patient has been assigned.

The distribution between the branches A (intensification with RAL) and B (placebo) will be 2:1.

It will be impossible for the investigators to know which group will be assigned to a patient before his/her inclusion in the study.

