### 5.4.2 Stratification

Randomization will be stratified by type of ART (PI/r/c or NRTI/NNRTI-based) and CD4 nadir (> 300 or < 300) at screening. In this way, the distribution of these parameters between the study groups will be balanced.

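### Section 10.1 ties no test to the primary endpoint; the Welch test on week-48 change that it implies is valid but leaves out baseline richness and the randomisation strata

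*Combined protocol and SAP*

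**What the plan says.** Section 5.3.1 defines the primary endpoint as "Increase in bacterial richness (observed species) at week 48, relative to baseline (week 0". Section 5.4.1 has participants "assigned sequentially into the two treatment groups (intensification with RAL or placebo", in a 2:1 ratio. Section 10.2 gives 40 on raltegravir and 20 on placebo, with no formal sample size calculation. Section 5.4.2 states "Randomization will be stratified by type of ART" and by CD4 nadir.

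The flow chart in Section 8.5 schedules stool samples at baseline and weeks 12, 24 and 48. Section 5.3.2 lists among the secondary endpoints "Longitudinal changes in" composition, function and further diversity indices.

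Section 10.1 says of the diversity measures: "This will enable comparisons between groups and timepoints". The univariate tests it names are:

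- for two groups: "2-group comparisons will be performed with the Welch's t-test";
- for more than two groups: "Univariate correlations involving >2 groups will be done applying ANOVA plus Tukey-Kramer post-hoc tests and Benjamini-Hochberg correction".

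No sentence ties either test to the primary endpoint. Neither baseline richness nor the strata appear anywhere in Section 10. The only factor to be taken into account is antibiotic intake (Section 6.7 adds supplements and drugs acting on immunity), and only in association analyses.

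**The concern.** A reader who wants to know how the primary endpoint will be tested has to assemble the answer: a change from baseline, two arms, and Welch for two-group comparisons. The result is an unadjusted comparison of mean change. Subtracting baseline uses each participant's own starting value, but with a coefficient fixed at 1, which over-corrects when the correlation between visits is below 1. Fitting the coefficient usually gives a more precise estimate from the same samples. It also protects better against a chance baseline difference, which matters with 20 participants on placebo.

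The design balances ART type and CD4 nadir, yet the analysis as written does not use them.

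There is a smaller gap beside this one. Comparisons across timepoints are announced, but no paired, repeated-measures or participant-blocked method is named, so that choice could be made after the data are seen.

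What is at stake for the primary endpoint is precision, not the error rate.

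**Working it through.** **Inputs from the documents.** 40 and 20 participants (Section 10.2); the primary endpoint is change from baseline to week 48 (Section 5.3.1). The plan gives no power figure to reproduce; its only arithmetic, 40 + 20 = 60 at 2:1, is consistent.

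**Assumed, because the documents do not give them.** Two-sided alpha 0.05, power 80%, normal data, SD = 1 at each visit, complete data, and correlation rho between baseline and week 48 of 0.3 to 0.9.

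**Step 1: variance per participant.** For week-48 richness minus b times baseline, the variance is 1 + b² − 2·b·rho.

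- Change score, b = 1: 2(1 − rho).
- Baseline-adjusted, b = rho (the minimum): 1 − rho².
- Ratio: (1 − rho²) / [2(1 − rho)] = (1 + rho)/2.

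**Step 2: detectable difference.** (1.960 + 0.842) × √(1/40 + 1/20) = 2.802 × 0.2739 = 0.767, multiplied by the square root of the variance in step 1. At rho 0.5, for example, this is 0.767 × √1.00 = 0.77 SD for change scores and 0.767 × √0.75 = 0.66 SD adjusted.

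**Step 3: equivalent sample size.** 60 / [(1 + rho)/2] is the number that the change-score test would need to match 60 participants with adjustment.

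| rho | Variance ratio | Detectable, change (SD) | Detectable, adjusted (SD) | Equivalent number |
|---|---|---|---|---|
| 0.3 | 0.65 | 0.91 | 0.73 | 92 |
| 0.5 | 0.75 | 0.77 | 0.66 | 80 |
| 0.7 | 0.85 | 0.59 | 0.55 | 71 |
| 0.9 | 0.95 | 0.34 | 0.33 | 63 |

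**Step 4: check by simulation.** The formulas ignore the cost of estimating the baseline slope and use normal rather than t quantiles. Simulation with 20,000 trials per value of rho, 40 against 20, includes both.

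| rho | Variance ratio | Power for 0.6 SD, change | Power for 0.6 SD, adjusted |
|---|---|---|---|
| 0.3 | 0.665 | 43.9% | 60.9% |
| 0.5 | 0.749 | 57.0% | 69.2% |
| 0.7 | 0.860 | 78.2% | 84.5% |
| 0.9 | 0.970 | 99.7% | 99.8% |

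Type I error was about 5% for both analyses at every rho.

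**Step 5: strata.** The documents do not say how strongly ART type or CD4 nadir predict richness, so no gain can be computed. In a simulation with two strata terms unrelated to the outcome, power stayed within 0.3 percentage points, so including them costs almost nothing.

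**Step 6: comparisons across visits.** This is a matter of text, not arithmetic. Section 10.1 does mention individuals, but only to say that "phylum abundance within individuals will be used to check for significant differences between groups"; that is a comparison between groups. Section 8.4 says that repeated stool samples allow for natural variation, which is a purpose without a method. Kernel regression is reserved for relations between the microbiome and the markers.

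**The case against.** The strongest reply is that the plan contains no error here. The Welch test on change is an inference from three sections, it holds its type I error, and preferring a baseline-adjusted model is advice on efficiency. This stands, and it sets the weight of the point.

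A second reply is that the gain depends on a correlation that nobody has stated. This also stands: at 0.9 the detectable difference moves only from 0.34 to 0.33 SD.

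A third is that this is a pilot exploratory study with no power target, and that Section 10.3 requires departures from the plan to be justified. The pilot status lowers the stakes. But Section 10.3 cannot guard a method that was never named, and a small trial has most use for precision that costs nothing.

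A reader might go further and infer that independent-sample tests will be run on raw values from repeated visits, or that visits will be pooled in a comparison of arms, so that error rates would be wrong. The documents do not say so. Section 10.1 attaches Welch and ANOVA to groups, not visits. It also supplies a possible third independent group, the HIV-negative profiles reported earlier by another consortium, so more than two groups need not mean more than two visits. For visit comparisons the plan omits a method; it does not state a wrong one.

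**Conclusion.** The point holds as a free improvement to the analysis and a gap in specification. The primary test is not stated. The one implied is valid, but less precise than an analysis of the same data adjusted for baseline richness, and it does not use the stratification factors. The variance falls by 35, 25, 15 or 5% at rho 0.3, 0.5, 0.7 or 0.9. These figures rest on normal data, equal SD at each visit and complete data; SD and rho are not in the documents. No numerical gain is claimed for the strata, and no distortion of the type I error is claimed. The missing within-person method is a secondary clarification.

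**What to change.** In Section 10.1, state the primary analysis as the raltegravir minus placebo difference in observed species at week 48, with its confidence interval, from a linear model with baseline richness, ART type and CD4 nadir stratum as covariates.

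Allow a mixed model over weeks 12, 24 and 48 with the same covariates where week-48 samples are missing, and state that it assumes data missing at random. That assumption needs a sentence of defence, because the reasons for early withdrawal in Section 7.3.1 include virological failure and intolerance.

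Add that any comparison across visits, including those of taxa and functions, will use paired or participant-blocked methods. Keep Welch and ANOVA for comparisons with one value per participant.

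Before CD4 nadir is used as a covariate, settle its definition: the two categories in Section 5.4.2 leave out a value of exactly 300, and the call to the CRO in Section 5.4.1 is said to report ART type but not nadir.

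Cost: some plan wording, a few lines of R and three degrees of freedom (one each for baseline richness, ART type and CD4 nadir). No new samples or visits.
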